6.3.1. Stratification

If participants are eligible for more than one ISA, they will be randomly assigned to an ISA using the IWRS. Participation in an ISA is not decided by the site, participant, or physician.

CCI [REDACTED]

Each ISA will include a stratification factor based on the average baseline pain severity score as measured by the NRS.

The definition of the stratification factor is provided as:

- severe pain: ≥ 7 on the baseline NRS average pain score, or
- moderate pain: < 7 on the baseline NRS average pain score.

Additional stratification factors may be defined in the ISA or DSA.

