9.4.2. Primary Endpoint and Analysis

The primary efficacy measure will be the same across all disease states and ISAs.

The primary efficacy analysis for an ISA will be conducted when all participants randomized to the ISA have completed the placebo-controlled portion of the ISA. The follow-up period may vary by ISA. Therefore, the primary efficacy analysis may be conducted prior to conclusion of the ISA and the collection of all follow-up data.

The primary efficacy analysis will be performed using a Bayesian MMRM method where the baseline information is modeled as a dependent variable. The baseline estimated means will be constrained to be the same between treatment groups due to randomization (Liang and Zeger, 2000). The primary efficacy analysis of the ISA of interest will be conducted on either the modified intention to treat (mITT) population or enhanced ITT population (see Section 9.3). The enhanced ITT population includes participant level data from ongoing ISAs and/or ISAs that have completed. Participants from ongoing ISAs must have had the opportunity to complete the placebo-controlled portion of the ISA to be included in the primary efficacy analysis for the ISA of interest. The ISA SAP will define the exact participant population included in the primary efficacy analysis.

The Bayesian CSF for the primary efficacy analysis will be defined in the ISA SAP for each respective ISA. The 95% credible intervals will be provided for the key parameters of interest.

This table describes information related to the primary efficacy measure.

Primary Efficacy Measure	Mean change from baseline to endpoint for average pain intensity as measured by the NRS. The exact endpoint for each ISA will be defined in the ISA SAP and may be defined, for example, as the last time point, the average of the last 2 time points, etc.
Data Collection	The NRS average pain will be collected daily. Average scores will be calculated over weekly and biweekly time intervals and will be available for analysis. The average of the weekly time-interval will be used for the primary efficacy analysis.
Primary Analysis	Efficacy of the active treatment(s) compared with placebo
Analysis Method	Bayesian MMRM analysis
Outcome Variable	The raw baseline and postbaseline values will be included in the response vector when fitting the statistical model. The change from baseline will be assessed via the statistical model.

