Fixed Categorical Effects in Model	
 • Time interval • Interaction of treatment by time interval without the baseline • Average baseline pain severity category (moderate or mild vs severe), defined by baseline NRS <7 vs baseline NRS ≥7 • Pooled investigative site
Additional Covariates in Model	Any stratification variable used for randomization of the ISA of interest will also be included in the model. Additional covariates may also be specified at an ISA level.

Abbreviations: ISA = intervention-specific appendix; MMRM = mixed-model repeated measures; NRS = numeric rating scale; SAP = statistical analysis plan.

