9.4.2.1. Key Features of the Bayesian Primary Efficacy Analysis Model

The primary efficacy analysis will be a Bayesian longitudinal MMRM analysis conducted on the NRS average pain score. The model will include the categorical effects and covariates described in Section 9.4.2. The change from baseline to each postbaseline time interval will be assessed.

The primary efficacy analysis model includes these key features:

- ability to borrow placebo information from other ISAs within the DSA using a suitable choice of informative prior on the key parameters
- ability to borrow treatment-effect information from other ISAs between DSA for the same intervention using a suitable choice of informative prior on the key parameters
- ability to update and tune the model parameters as more ISAs are added to the master protocol and more data become available
- flexibility for each ISA to define the amount of borrowing that will occur by specifying the prior distributions of key parameters in the ISA SAP
- ability to define which data from additional ISAs are included in the model
- flexibility to include additional covariates for each ISA as needed, and
- option to specify informative priors on some model parameters based on external data sources, for example, utilization of Bayesian Augmented Control for placebo parameters and data to inform other key parameters.

The ISA SAP will contain the exact specification of the model and parameters for the respective ISA.

Borrowing Strategy

Each ISA will define the specific decisions on the borrowing of placebo and treatment-effect information, including if borrowing will be implemented and, if so, how much information to borrow and the specific methodology used to borrow. These decisions may vary over the course of the master protocol, as some borrowing strategies may perform better than others as more data are available to borrow.

Specific differences between ISAs, for example, method of administration or additional inclusion or exclusion criteria, may impact the borrowing strategy for an ISA. Adjustments may also be made to the primary analysis model to incorporate the difference in placebo response in different time periods to facilitate efficient borrowing between the placebo participants.

The current borrowing strategies considered across the master protocol for each ISA include

- pooling of placebo data between ISAs within a disease state

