9.4.3.1. Continuous Efficacy Analyses

This table describes information related to the continuous secondary efficacy measures and analyses.

Key Secondary Measures	
 • NRS worst pain • VAS for pain • PGI • MOS Sleep Scale • EQ-5D-5L • Physical functioning—described in the DSA
Data Collection	The NRS worst pain will be collected daily. The scores for the other secondary measures will be collected at each visit as described in the visit schedule.
Analyses	Efficacy of active treatment(s) compared with placebo
Analysis Method	Same as primary efficacy analysis
Outcome Variable	The raw baseline and postbaseline values will be included in the response vector when fitting the

	statistical model. The change from baseline will be assessed via the statistical model
Fixed Categorical Effects in Model	
 • Time interval (or visit) • Interaction of treatment by time interval (or visit) without the baseline • Average baseline pain severity category (moderate vs severe), defined by baseline NRS <7 vs baseline NRS ≥7 • Pooled investigative site
Additional Covariates in Model	Additional covariates may also be specified at an ISA level.

Abbreviations: DSA = disease-state addenda; EQ-5D-5L = EuroQol-5D 5 level questionnaire; ISA = intervention-specific appendix; MOS = Medical Outcomes Study; NRS = numeric rating scale; PGI = Patient Global Impression of Change; VAS = visual analog scale.

In addition to the primary efficacy analysis of the NRS average pain score, the change from baseline to each postbaseline time interval (or visit) will be analyzed using a similar Bayesian MMRM method as the primary efficacy analysis for select scales. A similar participant population and borrowing strategy of the primary efficacy analysis for the ISA will be implemented for each scale. The ISA SAP will contain the exact specification of the model and parameters for each scale. The model will be fit for the following scales:

- NRS worst pain with weekly average values
- VAS, and
- physical functioning scales described in each DSA (note: direct treatment-effect borrowing will not be available for the physical functioning scales, since they are only collected within a DSA).

Similar borrowing and modeling may be considered for other efficacy scales. The ISA SAP will contain the exact specification of the model and parameters for each scale.

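### Minor: the primary model gives baseline severity one time-constant effect although baseline NRS is itself a response, which modestly overstates the standard error

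*Protocol*

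**What the plan says.** Section 9.4.2 specifies a Bayesian MMRM in which baseline is modelled as an outcome: "The raw baseline and postbaseline values will be included in the response vector when fitting the statistical model". Baseline means are held equal across arms. The table of fixed effects contains "Average baseline pain severity category (moderate or mild vs severe), defined by baseline NRS <7 vs baseline NRS ≥7". No severity-by-time term is listed, although the same table writes out the treatment-by-time interaction and excludes baseline from it.

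Section 9.4.2.1 makes the list binding, "The model will include the categorical effects and covariates described in Section 9.4.2", and also leaves detail to a later document: "The ISA SAP will contain the exact specification of the model and parameters for the respective ISA".

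Randomisation uses the same variable. Section 6.3.1 says "Each ISA will include a stratification factor based on the average baseline pain severity score as measured by the NRS", with the cut at 7. The endpoint may be, for example, "as the last time point, the average of the last 2 time points", and "The 95% credible intervals will be provided for the key parameters of interest". Under 9.1, success is a posterior probability exceeding a threshold.

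Section 9.4.3.1 repeats the term for the secondary measures: "Average baseline pain severity category (moderate vs severe), defined by baseline NRS <7 vs baseline NRS ≥7". Section 9.4.7 does add a subgroup-by-time term when severity is the subgroup. Of its three subgroup interactions, the one with time and the three-way one are marked as excluding baseline. The one with treatment is not.

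**The concern.** Severity is a dichotomy of one element of the response. At baseline the severe-versus-moderate gap is large by construction. After baseline, regression to the mean usually shrinks it. A single coefficient cannot fit both, so the misfit goes into the residual covariance.

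Because randomisation is stratified on severity, the arms are balanced on it and the estimate itself hardly moves. The model then reports more uncertainty than the estimate has. Part of the precision gained by stratifying is not credited in the credible interval, nor in the posterior probability that decides success. A second question is whether the misfit can move the estimate once that balance is lost through dropout or borrowed placebo data.

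**Working it through.** The protocol gives no SD, correlation, standard error or sample size (9.2 leaves sample size to each ISA), so there is no figure to reproduce. All numerical inputs below are assumptions.

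**When is a constant effect right?** If baseline and week-8 scores are jointly normal, the week-8 severity gap is the baseline gap times b = r × SD8 / SD0, where r is the baseline to week-8 correlation. The constant effect fits only when b is about 1. With SD0 = 1.6, SD8 = 2.1 and r = 0.3, b = 0.3 × 2.1 / 1.6 = 0.39. The simulated baseline gap of 2.61 should then fall to about 2.61 × 0.39 = 1.02; the simulated week-8 gap was 1.07.

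**Simulation, complete data.** Inputs: n = 150 at 2:1, permuted blocks within severity, 8 pooled sites, baseline mean 6.6, cut at 7, zero treatment effect, SD8 = 2.1, and correlation with baseline falling from 0.75 at week 1 to r at week 8. Fits were maximum likelihood with an unstructured 9 × 9 covariance (baseline plus 8 weeks), 2000 replicates per cell. Entries are b, then the model SE of the week-8 effect under the listed model divided by that under severity-by-time.

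| SD0 | r = 0.3 | r = 0.4 | r = 0.5 | r = 0.6 |
|---|---|---|---|---|
| 1.0 | 0.63; 1.012 | 0.84; 1.005 | 1.05; 1.004 | 1.26; 1.010 |
| 1.3 | 0.48; 1.032 | 0.65; 1.020 | 0.81; 1.009 | 0.97; 1.004 |
| 1.6 | 0.39; 1.060 | 0.53; 1.043 | 0.66; 1.028 | 0.79; 1.014 |

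The excess follows the distance of b from 1. The largest cell is 0.362 against 0.342 (0.343 with no severity term). For the mean of weeks 7 and 8 the ratios are 1.004-1.059.

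With SD8 closer to SD0 (SD0/SD8/r):
- 1.3/1.6/0.3: 1.067
- 1.6/1.8/0.3: 1.083
- 1.6/1.6/0.5: 1.077
- 1.6/1.6/0.3: 1.104

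**Is it precision or only its statement?** The ratio of actual sampling SDs was 0.999-1.002 in the table cells and 1.002-1.010 in the four further cells. Bias was at most 0.014. So the effect lies in the stated SE. Model SE over sampling SD, listed model versus severity-by-time (2500 replicates):
- SD0 1.3, r 0.3: 1.033 versus 1.001
- SD0 1.6, r 0.3: 1.040 versus 0.985
- SD0 1.6, SD8 1.6: 1.076 versus 0.982
- SD0 1.0, r 0.5: 0.979 versus 0.975

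**Separate runs with other inputs.** With baseline SD 1.2-1.6 and r = 0.2-0.65, large-sample ratios were 1.002-1.076. At n = 225 and r = 0.2, the sampling SD was 0.293 under both models, while the model SE was 0.305 (listed) against 0.288. Simulated power for a week-8 effect of -0.6 was 0.46 against 0.52. At r = 0.35 the figures were 0.285 against 0.276, and 0.55 against 0.58. Four further cells at n = 150 gave 1.003, 1.019, 1.061 and 1.109.

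**Dropout** (large sample, SD0 1.4, SD8 2.1, r = 0.2-0.5), as the difference between the two models' week-8 estimates:
- None, completely random, unequal between arms but unrelated to severity, severity-related but equal in both arms, or one response-based rule for both arms: 0.004 points or less.
- Related to severity or pain differently by arm (13-20% missing per arm): about 0.03-0.05 points, in either direction.
- Stress case, severe placebo participants leaving at 10% per week: bias of about -0.08 to -0.125 under the listed model, against about 0.02 or less in size with severity-by-time.

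**Pooled placebo.** Half the placebo group was taken from an ISA with baseline mean 0.3-0.6 higher, under a null effect. The listed model gave +0.05 to +0.11 at r = 0.3 and +0.01 to +0.04 at r = 0.5. Severity-by-time gave about 0.02 or less (Monte Carlo SE about 0.015).

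**NRS worst pain** (baseline correlation 0.85 with average pain): ratios 1.019-1.041, and 1.068 in the corner with both SDs 1.6 and r = 0.3. For a scale correlated 0.5: 1.008-1.015, and 1.022 in that corner.

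**The case against.** The best defence is that 9.4.2.1 leaves the exact model to the ISA SAP, 9.4.2 allows further covariates at ISA level, and listing a main effect does not forbid its interaction. This limits the point to the default list from which each ISA SAP starts. It does not remove it, because the protocol says the listed effects go into the model, writes interactions out where it means them, and gives the severity subgroup model a time interaction that the primary model lacks.

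Second, in the single-ISA setting the effect is conservative. An ISA that simulates the listed model under 9.2 already has it in its operating characteristics. That stands: it is an avoidable inefficiency, not an error in those characteristics.

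Third, every size rests on assumed inputs and on maximum likelihood without small-sample correction, priors or borrowing. Part of the ratio is also a slight understatement by the richer model: 1.040 against 0.985 in the cell with the 6.0% excess. That stands too.

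Fourth, dropping severity recovers practically the same SE (0.343 against 0.342). True, but 9.4.2 requires stratification variables in the model.

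A reader might infer that the primary analysis is biased or its false positive rate inflated. The documents do not support this: randomisation is stratified on the same category, and with complete or non-differential data the estimate barely moves. The opposite inference, that bias is impossible, fails as well. Missing values are imputed through the model (9.4.1.1) and placebo pooling is allowed (9.4.2.1), so the mean model can matter. Nor is 9.4.7 a true contradiction of the baseline constraint, since it carries over the 9.4.2 method; the unmarked term is a drafting inconsistency.

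**Conclusion.** The point holds as a minor one; the change is worth making but not essential. For a single ISA stratified on severity, with complete data or dropout that is not severity- or pain-related in an arm-specific way, the treatment estimate is practically unbiased. The model SE exceeds that of a severity-by-time model by about 0-6% at an assumed week-8 SD of 2.1. The excess reaches about 10% when that SD is near the baseline SD and correlation is low, and is 1% or less at correlation 0.5-0.6 with baseline SD 1.3 or less.

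Arm-specific severity- or pain-related dropout can shift the estimate by a few hundredths of an NRS point, and by about 0.1 in a stress case. Pooling placebo from ISAs with a different severity mix may do the same. Whether either arises cannot be seen from the protocol, which expects discontinuation to be uncommon (7.2) and leaves borrowing to each ISA. How far the SE figures carry over to a posterior with informative priors was not tested.

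**What to change.** In the 9.4.2 table, list *severity category* and *severity category by time interval*, keeping severity because it is a stratification factor. Make the same change for NRS worst pain in 9.4.3.1; for scales less correlated with baseline average pain it matters little.

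The cost is eight extra parameters (9 time points less 1) with their priors, and a rerun of any ISA simulations already done with the listed model. In the stratified runs the SE with the interaction was never larger than under the listed model or with no severity term, and 95% coverage was 0.940-0.952.

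Separately, and as wording only, mark the subgroup-by-treatment term in 9.4.7 as excluding baseline, like its two neighbours, or delete it. It then cannot be read against the equal-baseline constraint of 9.4.2.

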9.4.2.1. Key Features of the Bayesian Primary Efficacy Analysis Model

The primary efficacy analysis will be a Bayesian longitudinal MMRM analysis conducted on the NRS average pain score. The model will include the categorical effects and covariates described in Section 9.4.2. The change from baseline to each postbaseline time interval will be assessed.

The primary efficacy analysis model includes these key features:

- ability to borrow placebo information from other ISAs within the DSA using a suitable choice of informative prior on the key parameters
- ability to borrow treatment-effect information from other ISAs between DSA for the same intervention using a suitable choice of informative prior on the key parameters
- ability to update and tune the model parameters as more ISAs are added to the master protocol and more data become available
- flexibility for each ISA to define the amount of borrowing that will occur by specifying the prior distributions of key parameters in the ISA SAP
- ability to define which data from additional ISAs are included in the model
- flexibility to include additional covariates for each ISA as needed, and
- option to specify informative priors on some model parameters based on external data sources, for example, utilization of Bayesian Augmented Control for placebo parameters and data to inform other key parameters.

The ISA SAP will contain the exact specification of the model and parameters for the respective ISA.

Borrowing Strategy

Each ISA will define the specific decisions on the borrowing of placebo and treatment-effect information, including if borrowing will be implemented and, if so, how much information to borrow and the specific methodology used to borrow. These decisions may vary over the course of the master protocol, as some borrowing strategies may perform better than others as more data are available to borrow.

Specific differences between ISAs, for example, method of administration or additional inclusion or exclusion criteria, may impact the borrowing strategy for an ISA. Adjustments may also be made to the primary analysis model to incorporate the difference in placebo response in different time periods to facilitate efficient borrowing between the placebo participants.

The current borrowing strategies considered across the master protocol for each ISA include

- pooling of placebo data between ISAs within a disease state
 - note: pooling is not being considered for borrowing treatment-effect information for an intervention studied in multiple disease states
- use of a hierarchical model with an appropriate prior on the between-study standard deviation (SD) (or variance) term that influences the amount of borrowing
- commensurate priors with different mixture probability weights
- mixture priors
- meta-analytic predictive prior or meta-analytic combined prior, and
- model fit with respective ISA data only (no utilization of information from other ISAs).

9.4.3. Secondary Endpoints and Analysis

The secondary efficacy measures will be the same across all disease states and ISAs.

9.4.3.1. Continuous Efficacy Analyses

This table describes information related to the continuous secondary efficacy measures and analyses.

Key Secondary Measures	
 • NRS worst pain • VAS for pain • PGI • MOS Sleep Scale • EQ-5D-5L • Physical functioning—described in the DSA
Data Collection	The NRS worst pain will be collected daily. The scores for the other secondary measures will be collected at each visit as described in the visit schedule.
Analyses	Efficacy of active treatment(s) compared with placebo
Analysis Method	Same as primary efficacy analysis
Outcome Variable	The raw baseline and postbaseline values will be included in the response vector when fitting the

	statistical model. The change from baseline will be assessed via the statistical model
Fixed Categorical Effects in Model	
 • Time interval (or visit) • Interaction of treatment by time interval (or visit) without the baseline • Average baseline pain severity category (moderate vs severe), defined by baseline NRS <7 vs baseline NRS ≥7 • Pooled investigative site
Additional Covariates in Model	Additional covariates may also be specified at an ISA level.

Abbreviations: DSA = disease-state addenda; EQ-5D-5L = EuroQol-5D 5 level questionnaire; ISA = intervention-specific appendix; MOS = Medical Outcomes Study; NRS = numeric rating scale; PGI = Patient Global Impression of Change; VAS = visual analog scale.

In addition to the primary efficacy analysis of the NRS average pain score, the change from baseline to each postbaseline time interval (or visit) will be analyzed using a similar Bayesian MMRM method as the primary efficacy analysis for select scales. A similar participant population and borrowing strategy of the primary efficacy analysis for the ISA will be implemented for each scale. The ISA SAP will contain the exact specification of the model and parameters for each scale. The model will be fit for the following scales:

- NRS worst pain with weekly average values
- VAS, and
- physical functioning scales described in each DSA (note: direct treatment-effect borrowing will not be available for the physical functioning scales, since they are only collected within a DSA).

Similar borrowing and modeling may be considered for other efficacy scales. The ISA SAP will contain the exact specification of the model and parameters for each scale.

Additional analyses will be conducted using data only from the respective ISA, which do not utilize any borrowing of placebo and/or treatment information. A Bayesian MMRM analysis will be used to evaluate the change from baseline to each postbaseline time interval (or visit) and the comparison of treatment groups within an ISA for

- NRS average pain
- NRS worst pain
- VAS
- physical functioning scales described in each DSA
- PGI
- EQ-5D-5L, and
- MOS Sleep Scale multi-item scores of sleep disturbance, somnolence, sleep adequacy, and the sleep problems index.

The Bayesian models will include the categorical effects and covariates described in Section 9.4.3, unless otherwise noted in the ISA SAP.

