9.4.3.2. Categorical Efficacy Analyses

The proportion of participants in each treatment group meeting prespecified binary efficacy outcomes will be estimated for each postbaseline visit. The estimates will be provided from a longitudinal Bayesian model that includes all postbaseline observations. The average weekly score for the NRS will be computed and used in the comparison between treatment groups within an ISA.

The prespecified binary efficacy outcomes include the proportion of participants

- with a pain reduction greater than or equal to 30%, 50%, and 70% from baseline as measured by the NRS average pain scale
- with a pain reduction greater than or equal to 30%, 50%, and 70% from baseline as measured by the NRS worst pain scale
- with a pain reduction greater than or equal to 30%, 50%, and 70% from baseline as measured by the VAS
- with at least 2-point reduction from baseline on the NRS average pain scale
- with at least 2-point reduction from baseline on the NRS worst pain scale, and
- with an improvement in physical function greater than or equal to 30%, 50%, and 70% from baseline as measured by the physical functioning scales defined in the DSA.

The models will include treatment, time interval (or visit), interaction between treatment by time interval (or visit), average baseline pain severity category (moderate vs severe) as defined by baseline NRS less than 7 versus baseline NRS greater than or equal to 7 and pooled investigative site, unless otherwise noted in the ISA SAP. The ISA SAP will contain the exact specification of the model and parameters for the respective ISA.

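### Randomisation strata are compulsory in the primary model but not required in the default secondary and responder models

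*Protocol*

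**What the plan says.** **Strata.** Section 6.3.1 fixes one factor for the whole platform: "Each ISA will include a stratification factor based on the average baseline pain severity score as measured by the NRS". It then leaves room for more: "Additional stratification factors may be defined in the ISA or DSA".

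**Primary model.** The covariate row in Section 9.4.2 is a rule: "Any stratification variable used for randomization of the ISA of interest will also be included in the model". A separate sentence in the same row allows further ISA-level covariates.

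**Continuous secondary measures.** The corresponding row in Section 9.4.3.1 has lost the rule and keeps only the permission: "Additional covariates may also be specified at an ISA level". The same table gives the analysis method as "Same as primary efficacy analysis", and the text below it states "The ISA SAP will contain the exact specification of the model and parameters for each scale".

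**No-borrowing models.** These cover NRS average pain as well as the other scales. Section 9.4.3.1 says of them: "The Bayesian models will include the categorical effects and covariates described in Section 9.4.3, unless otherwise noted in the ISA SAP".

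**Responder models.** The covariate sentence in Section 9.4.3.2 opens with "The models will include treatment, time interval (or visit), interaction between treatment by time interval (or visit" and goes on to baseline pain severity category and pooled site. It names no other stratification factor, and it too lets the ISA SAP depart from the list.

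**The concern.** The protocol is not silent here. It sets one rule for the primary model and a weaker default for the rest. An ISA SAP that writes nothing further on covariates inherits a primary model with the added stratum and secondary models without it.

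Stratified randomisation balances the arms on the factor and so reduces the true sampling variance of the treatment contrast. A linear model that leaves the factor out puts its variance into the residual and reports more uncertainty than there is.

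The clearest case is NRS average pain. It is analysed once as the primary endpoint, possibly with borrowing, and again with the ISA's own data only. If the two models also differ in covariates, their comparison no longer isolates borrowing, whose impact Section 9.4.8 says will be evaluated.

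**Working it through.** The master protocol gives no sample size, SD, effect size or power (Section 9.2 leaves these to each ISA), so there is no figure to reproduce. The effect sizes below rest on assumptions, and frequentist models stand in for the Bayesian models with vague priors.

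**Step 1: default treatment of an added factor**

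| Model | Pain severity | Added stratification factor |
|---|---|---|
| Primary, 9.4.2 | included | required |
| Continuous secondary, 9.4.3.1 | included | permitted |
| No-borrowing, 9.4.3.1 (includes NRS average pain) | included | permitted, or by ISA SAP departure |
| Responder, 9.4.3.2 | included | only by ISA SAP departure |

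**Step 2: continuous endpoints, closed form.** Let R² be the share of the variance remaining after the retained covariates that the omitted, balanced factor explains. Then:

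- model SE / true SD of the estimate: k = 1/√(1 − R²)
- actual coverage of a nominal 95% interval: 2Φ(1.960k) − 1
- power, starting from an assumed 80% at two-sided 0.05: Φ(1.960 + 0.842 − 1.960k)

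| Assumed R² | k | Coverage | Power |
|---|---|---|---|
| 0 | 1.000 | 95.0% | 80.0% |
| 0.02 | 1.010 | 95.2% | 79.4% |
| 0.05 | 1.026 | 95.6% | 78.5% |
| 0.10 | 1.054 | 96.1% | 76.9% |
| 0.20 | 1.118 | 97.2% | 72.9% |

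**Step 3: simulation check.** The settings were total N of 100 and 200, 1:1 allocation within two equal strata, baseline correlation 0.5 and 4,000 runs. Here the factor's share was set on total variance. Baseline takes 0.5² = 0.25 of that, so the share of the remainder is the set value divided by 0.75.

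| Share of total | Share of remainder | k by formula | Simulated, N = 100 / 200 |
|---|---|---|---|
| 0.02 | 0.027 | 1.014 | 1.015 / 1.010 |
| 0.05 | 0.067 | 1.035 | 1.029 / 1.033 |
| 0.10 | 0.133 | 1.074 | 1.069 / 1.058 |
| 0.20 | 0.267 | 1.168 | 1.152 / 1.169 |

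Formula and simulation agree. With these non-zero factors included in the model, coverage was 94.5% to 95.0%.

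**Step 4: responder endpoints.** The protocol does not fix the link, so a logit is assumed. The simulation used a single time point, total N of 200, a conditional log odds ratio of 0.8 and 1,500 runs.

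| Control rates in the two strata | Model | Estimate | Model SE | Sampling SD | Rejection rate |
|---|---|---|---|---|---|
| 25% vs 60% | without factor | 0.697 | 0.289 | 0.270 | 72.1% |
| 25% vs 60% | with factor | 0.807 | 0.314 | 0.315 | 74.2% |
| 35% vs 50% | without factor | 0.792 | 0.290 | 0.279 | 80.6% |
| 35% vs 50% | with factor | 0.816 | 0.295 | 0.289 | 80.6% |

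Leaving the factor out shrinks the estimate by 14% (1 − 0.697/0.807) in the stronger case and by 3% (1 − 0.792/0.816) in the milder one. The SE is smaller than the adjusted SE in both. In the stronger case it is still about 7% above the estimate's own sampling SD (0.289/0.270 = 1.07).

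**The case against.** The strongest reply is that this is ISA SAP territory. An added factor would first appear in an ISA or DSA. The ISA SAP specifies that ISA's models and, under Section 9.4.1, prevails over the master SAP. Section 9.4.3.1 permits extra covariates and calls the method the same as the primary. The no-borrowing and responder lists both yield to the ISA SAP. The one factor every ISA must use, pain severity, is already in all these models.

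Most of that stands, and it rules out three stronger readings that a reader might infer:

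- **That the secondary and responder models exclude added strata, or that the responder list is closed.** The text permits the terms or lets the ISA SAP add them. It only fails to require them.
- **That Section 6.3.1 expects further factors.** It says they may be defined, no more.
- **That the error bars are too wide in every one of these models.** For log-odds responder models the SE without the factor is smaller than the adjusted one. The main effect is on the estimate.

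The reply does not explain why a rule stated for the primary model is missing from a parallel table whose method row claims equivalence. In Section 9.4.2 the permissive sentence stands beside the rule as an addition to it, so it cannot be read as a substitute. A reader cannot tell whether the omission is meant.

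A blanket requirement would also have a cost. Responder models at the 70% threshold with pooled site may be sparse, and some freedom to simplify them should remain.

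**Conclusion.** The inconsistency is real and minor. It has an effect only if three things coincide: an ISA or DSA adds a stratification factor, the ISA SAP keeps the default covariates, and the factor is prognostic beyond pain severity, site and the modelled baseline.

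Continuous secondary intervals would then be conservative, with SEs about 1%, 3% or 5% too large at an assumed residual R² of 0.02, 0.05 or 0.10. Responder log odds ratios could be attenuated, by 3% and 14% in the two simulated cases. The primary and no-borrowing analyses of NRS average pain could differ in covariates as well as in borrowing.

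No ISA that adds no factor is affected. The primary analysis and the critical success factor are unaffected throughout.

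**What to change.** Add the Section 9.4.2 sentence, "Any stratification variable used for randomization of the ISA of interest will also be included in the model", to the covariate row in Section 9.4.3.1 and to the model sentence in Section 9.4.3.2. The no-borrowing models then pick it up through their reference to Section 9.4.3. In 9.4.3.2, keep the existing clause that lets the ISA SAP depart from the list, so that a sparse responder model can be simplified with a stated reason.

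The cost is two sentences. No new data are needed and the primary analysis does not change. Each later ISA SAP is also spared having to remember to add the term, on a platform expected to admit interventions for 5 to 7 years (Section 4.1).
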